where ORR is defined as a CR or PR. Patients without a post-baseline disease assessment will be considered as non-responders. The analysis population for ORR will be all enrolled patients with measurable disease at baseline. An estimate of ORR and its 95% CI will be calculated using the Blyth-Still-Casella method for each treatment arm. CIs for the difference in ORRs between the subgroups will be determined using the normal approximation to the binomial distribution. In addition, ORR is analyzed with a generalized logistic regression analysis. Subgroup is included as fixed effect, KPS as a covariate and study center as random effect. The adjusted odds ratio for being a responder is estimated and the two-sided 95% confidence interval presented.

DOR is defined as the time from the initial response to disease progression or death among patients who have experienced a CR or PR during study. Patients who have not progressed or died at the time of analysis will be censored at the last disease assessment date. DOR will be estimated using Kaplan- Meier methodology. Comparisons between subgroups through use of the unstratified log-rank test will be made for descriptive purposes only.

- To evaluate the efficacy of tesevatinib as measured by PFS-6, OS-9, RANO ORR and DOR in the subgroups:
  - EGFRvIIIpos vs EGFRvIIIneg
  - EGFR amplificationpos vs EGFR amplificationneg

The statistics for these subgroup comparisons are described at each of the endpoints.

In addition, statistics for the change and percent change from baseline tumor measurements will be presented. These analyses will be done after each two cycles of therapy. Summary statistics will be produced for PFS and OS. The percentage of patients without disease progression after 3 and 6 months of dosing will also be presented separately by local (investigator) and potentially by central radiography results. Sites will provide copies of all MRI image sets for central retention in case central radiology review is required.

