#### 3.1.4.3 Progression-Free Survival (PFS) Endpoints

PFS is defined as the time from date of first dose to the date of disease progression or death, whichever happens first. For subjects who do not have an event (i.e. those who have not progressed, and are alive at the date of data cut-off or lost to follow-up), progression-free survival will be censored on that date.

PFS will be summarized using Kaplan-Meier methods for 25th percentile, median, and 75th percentile. 95% Confidence intervals will be calculated using Greenwood Formulation. Kaplan-Meier curves will be plotted for populations in the analysis.

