## 3.8.2.5 Objective Response Rate (ORR) and DOR per RANO

ORR including CR or PR per RANO criteria will be analyzed with method as described in 3.1.4.2 respectively in subpopulations A and B, and in mITT population. This analysis will be performed in subpopulations A and B, and in mITT population.

For responders in above analyses, corresponding Duration of response is calculated as the time from first documented evidence of CR or PR (whichever status is recorded first) until the first documented sign of disease progression or death due to any cause (whichever is the first). DOR will be summarized

It is defined for subjects with a confirmed CR or a confirmed PR. For subjects in the subset of responders who do not progress or die, duration of response will be analyzed with method as described in 3.1.4.3.

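### SAP 3.8.2.5 assigns a method for duration of response only to responders without an event, and the section it points to censors later than the protocol does

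*SAP*

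**What the plan says.** SAP 3.8.2.5 first defines the endpoint. The start of the clock is clear: "Duration of response is calculated as the time from first documented evidence of CR or PR (whichever status is recorded first"). The event is clear too: the clock stops at progression or at death from any cause, if that comes earlier. The population follows: "It is defined for subjects with a confirmed CR or a confirmed PR".

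The method is less clear. One sentence says only "DOR will be summarized" and names no estimator. The next statement on method is: "For subjects in the subset of responders who do not progress or die, duration of response will be analyzed with method as described in 3.1.4.3".

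SAP 3.1.4.3, the section referred to, is written for progression-free survival (PFS). For subjects still event-free at data cut-off or lost to follow-up, it says "progression-free survival will be censored on that date". It then asks for Kaplan-Meier quartiles with Greenwood intervals.

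Protocol 13.4.6.2 gives a complete rule for DOR. The clock starts at the initial response, the population is every patient with a CR or PR, and patients without progression or death are censored at the last disease assessment. It adds: "DOR will be estimated using Kaplan- Meier methodology".

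SAP 3.1.2 says in general terms that methods were changed from the protocol where needed. It lists no individual change.

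**The concern.** A programmer working from the SAP has one instruction on how to analyse DOR, and it names the wrong set of patients. Responders who progressed or died supply all the information on how long responses last, and the sentence does not send them to any method. If it is instead taken as a censoring rule, it brings in the PFS censoring date, which differs from the protocol's date for DOR.

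DOR is a secondary objective in all patients and in both EGFR subpopulations, and SAP 3.8.2.6 asks for DOR comparisons by EGFR status without naming a method. With few responders, the handling of a single patient can move the curve. Because SAP 3.1.2 lists no changes, a reader cannot tell whether the departure from the protocol is deliberate.

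**Working it through.** The plan states no response rate, DOR assumption, event count or power for DOR, so there is no figure to reproduce. The check compares the two documents and then works through the two readings.

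**The rules side by side**

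| Item | Protocol 13.4.6.2 | SAP 3.8.2.5 with 3.1.4.3 |
|---|---|---|
| Clock starts | Initial response | First documented CR or PR |
| Event | Progression or death | Progression or death |
| Patients given a method | All with CR or PR | Only those without an event |
| Censoring date | Last disease assessment | Data cut-off or loss to follow-up |
| Estimator | Kaplan-Meier | Kaplan-Meier, by reference |

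The clock and the event agree. The patients given a method and the censoring date do not.

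**Literal reading**

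The Kaplan-Meier estimate is S(t) = product over event times of (1 − d/n), where d is the number of events and n the number at risk. Greenwood's variance is S(t)² × sum of d/[n(n − d)]. If the set holds only patients without an event, there are no event times. The product is then empty, so S(t) = 1 throughout; the sum is empty, so the variance is 0. No quartile is reached. This needs no assumption about the data.

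**Illustration (assumed data, not from the documents)**

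Take 8 responders. Five have events at 2, 3, 4, 5 and 7 months from response. Three are event-free, with last assessments at 6, 9 and 10 months.

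- Literal subset: 3 patients, 0 events, no quartiles.
- Protocol rule, all 8 responders: S(2) = 7/8 = 0.875; S(3) = 0.875 × 6/7 = 0.75; S(4) = 0.75 × 5/6 = 0.625; S(5) = 0.625 × 4/5 = 0.50. The 6-month patient is then censored, leaving 3 at risk, so S(7) = 0.50 × 2/3 = 0.333. The curve is level at 0.50 from 5 to 7 months, and software that requires a fall below 0.50 reports a median of 7.0 months.

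The same patients therefore give an estimate under the protocol rule and none under the literal SAP sentence.

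**Charitable reading: event-free responders censored as in 3.1.4.3**

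The protocol schedules assessments at Weeks 4 and 8 and then every 8 weeks. For an event-free responder who is on schedule, the gap between last assessment and data cut-off is at most 8 × 7 = 56 days, or 56/30.4 = 1.84 months. It can be longer if assessments were missed or had stopped.

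In the illustration, suppose the patient last assessed at 6 months is censored at cut-off, 6 + 1.84 = 7.84 months. That patient is now at risk at 7 months, so S(7) = 0.50 × 3/4 = 0.375 instead of 0.333. With a gap under 1 month nothing changes. The shift is between 0 and 0.042 here, and the reported median stays the same. The direction is general: later censoring dates with the same events can only hold the curve level or raise it, so DOR looks no shorter and may look longer.

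**Number of responders**

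At an assumed response rate of 5% to 25%, 40 patients give 40 × 0.05 = 2 to 40 × 0.25 = 10 responders.

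**The case against.** The strongest reply is that nobody would run Kaplan-Meier on a set in which no event is possible. SAP 3.8.2.5 defines DOR to progression or death for all confirmed responders, and its method sentence closely tracks the wording that 3.1.4.3 uses for subjects to be censored. The natural reading is that event-free responders are censored as in that section. Protocol 13.4.6.2 would also settle any doubt. This is fair, and the charitable reading is probably the intended one. It does not close the point, because that reading brings in the different censoring date.

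The short sentence on summarising DOR also ends without a full stop, so words may have been lost when the PDF was read. If the source file names a method for all responders there, the literal reading falls. The censoring date would still differ unless the missing words deal with it.

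Three stronger conclusions are tempting, and the documents do not support them:

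- **That DOR would be timed from first dose.** SAP 3.1.4.3 does say "PFS is defined as the time from date of first dose to the date of disease progression or death, whichever happens first", but this defines PFS. SAP 3.8.2.5 gives DOR its own start at first documented response and cites 3.1.4.3 only for its method. A change of clock would move times and would not remove events.
- **That DOR cannot be estimated at all.** Only the analysis as literally worded is empty. The SAP definition and the protocol rule together support an ordinary estimate.
- **That reported DOR will be too short by a given amount.** This would require the responders with events to be summarised alone and that figure reported as DOR. The SAP specifies no such split, and the documents give no response rate, DOR or censoring pattern from which to size it.

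**Conclusion.** The sentence is defective on either reading. Taken literally, it yields zero events and no quartiles; that follows from the wording alone. Taken as a censoring rule, it replaces the protocol's date with a later one, counts unassessed time as response, and is not listed as a change in SAP 3.1.2. The size of the second effect rests on the 8-week schedule being kept: at most about 1.8 months of added follow-up per event-free responder, with a small or no shift in the curve in the assumed example.

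The importance is low to moderate. DOR is a secondary endpoint, the study has no power for secondary endpoints, the protocol makes its DOR comparisons for description only, and few responders are likely. The primary analysis is not affected.

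**What to change.** Replace the method sentence in SAP 3.8.2.5 with:

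> DOR is measured from first documented CR or PR (confirmed) to progression or death and is estimated by Kaplan-Meier in all confirmed responders; responders without progression or death are censored at the last disease assessment, as in protocol 13.4.6.2.

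Remove or complete the unfinished sentence on summarising DOR at the same time. If the sponsor does intend to censor at data cut-off or loss to follow-up, SAP 3.1.2 should list that as a change from the protocol and give the reason.

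The cost is one SAP sentence. Disease assessment dates are already collected, so no new data and no protocol amendment are needed.

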#### 3.8.2.6 PFS-6, OS-9, ORR and DOR comparisons in the following subgroups

- EGFRvIIIpos vs EGFRvIIIneg
- EGFR amplificationpos vs EGFR amplificationneg

## 3.9 Patient-Reported Outcomes (PRO)

Patient-reported outcomes in M.D. Anderson Symptom Inventory – Brain Tumor questionnaire (MDASI-BT) will be listed for teach subject.

## 3.10 Safety Analysis

Safety assessments will include AEs, serious adverse events (SAEs), vital sign measurements, clinical laboratory evaluations (hematology and chemistry), and electrocardiograms (ECGs). Unscheduled visits for safety assessments will not be presented in summary tables but will be in listings. All safety analyses will be performed using the safety population.

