# **Clinically Significant (CS) Laboratory Abnormalities**

Any laboratory abnormality that is considered to be clinically significant by the investigator will be recorded on the AE eCRF. A clinically significant abnormal test result will be considered an AE if:

• It is not associated with an already reported AE, diagnosis or pre-existing condition

- There is a change in concomitant medication or intervention as needed, in direct response to the laboratory result
- The investigator exercises his/her discretion to make significance determinations for any patient laboratory result or result that requires intervention

All such lab abnormalities will be repeated and assessed by the investigator, or licensed (MD), as soon as possible for "seriousness" and if they meet the regulatory definition of "serious", they will be reported as SAEs following regulatory and protocol requirements. Repeat laboratory tests may be run in order to monitor the result.

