## 13.4.6.5. Safety Data

Safety analyses will be performed on all patients who received any quantity of study drug. AEs that are not related to treatment and that occur more than 30 days after the administration of the last dose of treatment will not be reported or analyzed.

Safety analyses will present overall results and results by subgroups.

Safety observations and measurements include AEs, safety laboratory tests, vital sign measurements, physical examinations, ECG assessments, and plasma levels.

Treatment-emergent AEs will be summarized using MedDRA® (Version 18.1 or higher) System Organ Class (SOC) and preferred term, classified from verbatim terms. The incidence and percentage of patients with at least 1 occurrence of a preferred term will be included, according to the most severe grade using the NCI-CTCAE; Version 4.03. The number of events per

preferred term will also be summarized. Causality (relationship to study treatment) will be summarized separately.

AEs, SAEs, related AEs, related SAEs,  $\geq$  Grade 3 AEs, related  $\geq$  Grade 3 AEs, and AEs leading to withdrawal, dose modification, or treatment discontinuation will be summarized by subgroup and tesevatinib overall according to SOC and preferred terms. All AEs will be in listings. Duration of AEs will be determined and included in listings, along with action taken and outcome.

Laboratory results will be classified according to NCI-CTCAE Version 4.03 and summarized. Laboratory results not corresponding to a coded term will not be graded. Incidence of laboratory abnormalities will be summarized. The worst on-study grade after the first dose of study drug will be summarized. The incidence of  $\geq$  Grade 3 laboratory abnormalities under treatment and shifts in toxicity grading from baseline to highest grade post-baseline will be displayed. Results for variables that are not coded will be presented in the listings as below, within, and above the normal limits of the local laboratory.

Vital sign measurements will be summarized at each scheduled time point using descriptive statistics. Karnofsky performance status results will be summarized by scheduled time point. Additional statistical details will be provided in a prospective statistical plan.

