Digital ECG results and wave intervals measurements will be summarized and reported by patient visit and dose cohort and/or as appropriate. QTc prolongation results will be summarized separately. Covariate analyses will be employed as necessary.

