## 3.10.2 Clinical Laboratory Evaluation

The summary statistics (including number, mean, standard deviation, median, minimum and maximum) of all laboratory variables and changes from baseline will be calculated for each visit or study assessment by treatment group. For parameters of white blood cell counts, neutrophils (absolute count), lymphocytes (absolute count), monocytes (absolute count), hemoglobin, platelets, ALP, ALT, aspartate aminotransaminase, gamma glutamyl transferase, total bilirubin, glomerular filtration rate, plots of mean/mean changes from baseline with the corresponding standard error will be displayed.

For shift tables, laboratory results will be classified using the CTCAE Version 4.03. All graded laboratory parameters will be summarized separately for hematology and biochemistry. Corresponding shift tables comparing baseline to the worst post-baseline grade within the treatment period will be provided.

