#### 3.10.4 ECG

Descriptive statistics for ECG parameters (i.e., PR interval, QRS interval, and QTcF interval) at each time point with triplicate ECGs will be presented for the values and

change from baseline scores. (QTcF is the QT interval using Fridericia's correction which is calculated by  $QTcF = QT/RR^{1/3}$ .)

The number and percentage of subjects with observed QTcF values that satisfy the following conditions will be presented by treatment group and study visit and categorized as:  $\leq 450$  ms; > 450 to 480 ms; > 480 to 500 ms; and > 500 ms.

The number and percentage of subjects having change from baseline QTcF values that satisfy the following conditions will be presented by treatment group and study visit and categorized as:  $\leq 0$  ms; > 0 to  $\leq 30$  ms; > 30 to  $\leq 60$  ms; and > 60 ms.

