## 4 LIST OF TABLES, FIGURES, AND LISTINGS

List of tables, figures, and listings will be completed in a separate document.

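### SAP 3.10 keeps unscheduled visits out of safety summary tables without exception, which read literally conflicts with the worst-grade laboratory tables; separately, the SAP specifies no any-time QTcF summary

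*SAP*

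**What the plan says.** SAP 3.10 lists the safety assessments as adverse events, serious adverse events, vital signs, laboratory evaluations and ECGs. It then says: "Unscheduled visits for safety assessments will not be presented in summary tables but will be in listings". No later part of 3.10 qualifies this.

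**Laboratory tables.** SAP 3.10.2 says: "Corresponding shift tables comparing baseline to the worst post-baseline grade within the treatment period will be provided". Protocol 13.4.6.5 says: "The worst on-study grade after the first dose of study drug will be summarized". It also plans the incidence of ≥ "Grade 3 laboratory abnormalities under treatment and shifts in toxicity grading from baseline to highest grade post-baseline will be displayed". None of these is limited to scheduled visits.

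**QTcF tables.** SAP 3.10.4 says: "The number and percentage of subjects with observed QTcF values that satisfy the following conditions will be presented by treatment group and study visit". The change-from-baseline categories are laid out the same way. Protocol 13.4.6.5 says: "QTc prolongation results will be summarized separately", without giving a form. The table shells are not in the SAP: "List of tables, figures, and listings will be completed in a separate document" (SAP section 4).

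**The concern.** A worst-grade table is meant to show the most abnormal value each patient had on treatment. Off-schedule samples are often taken because something looks wrong, so leaving them out is not neutral. If a patient's worst laboratory value was drawn at an unscheduled visit, a programmer cannot follow both SAP 3.10 and SAP 3.10.2. Following 3.10 leaves that value in a listing, and the tabulated incidence is too low.

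Safety and tolerability is a primary objective (protocol 6.1.2), and QTc prolongation is an adverse event of special interest (protocol 9.1.4). For QTcF the question is different: whether the plan gives a reader the proportion of patients who reached each category at any time on treatment.

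**Working it through.** The plan states no figure on this point, so the check is a comparison of texts plus simple proportions.

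**1. Do off-schedule values arise?** Yes.
- On clinically significant laboratory results, protocol 11.3.9 says: "All such lab abnormalities will be repeated and assessed by the investigator, or licensed (MD), as soon as possible". The triggering value may itself be scheduled, so only a repeat with a worse grade matters here.
- Protocol 12.2.15 allows hematology, chemistry and triplicate ECGs at unscheduled visits.
- Protocol 9.1.4.3 calls for an ECG when symptoms of arrhythmia or syncope occur.

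**2. Which panels leave more room for them?** These are scheduled draws after Day 1 through Cycle 6, with 28-day cycles and no delays (protocol Table 1 with footnote e, and 12.2.11):

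| Panel | Study days | Number | Gap |
|---|---|---|---|
| Chemistry | 15, 29, 43, 57, 71, 85, 99, 113, 127, 141, 155 | 11 | 14 days |
| Hematology | 15, 29, 57, 85, 113, 141 | 6 | 28 days from Day 29 |

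The Day 15 draws in Cycles 2 to 6 are chemistry only, so hematology has the longer gap. This shows where exposure lies. It does not show how often a worst grade falls off schedule.

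**3. Direction of the effect.** For one patient and one parameter, let S be the scheduled post-baseline grades and U the unscheduled ones. Then max(S) ≤ max(S and U together). Dropping U can move the patient to a lower worst grade, never a higher one. The proportion at or above any grade can therefore only fall or stay the same.

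**4. Size per patient.** With 40 planned patients, k patients whose Grade 3 or higher result was seen only off schedule lower that incidence by k/40. For k = 1 this is 1/40 = 2.5 percentage points. As an illustration, with Clopper-Pearson 95% intervals, the laboratory table would show 0/40 (0 to 8.8%) instead of 1/40 (2.5%; 0.06 to 13.2%). The documents give no basis for choosing k.

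**5. How far does the literal rule reach?** Adverse events are on the SAP 3.10 list of safety assessments. Read literally, the rule would also remove events found at unscheduled visits from the adverse event tables. Protocol 11.2 expressly requires such events to be recorded.

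**6. QTcF: what the other tables recover.**
- Protocol 9.1.4.3.1 sets actions for a rise of at least 60 ms and for values of at least 500 ms.
- Protocol 12.1.9 requires further monitoring for a rise above 60 ms or a value of at least 500 ms. It sends ECG abnormalities to the adverse event form if they change management or produce signs and symptoms; the second limb has no numeric threshold.
- SAP 3.10.1 tabulates those events.
- An off-schedule value below 500 ms with a rise below 60 ms, and with neither symptoms nor a change in management, would appear only in a listing. Such values can fall in the SAP's categories of more than 450 to 480 ms, more than 480 to 500 ms, or a rise of more than 30 to 60 ms.
- The weekly ECGs for two weeks after restart at a reduced dose are required by protocol 9.1.4.3.1 and Table 1 footnote h. They have no column of their own in Table 1, and SAP 3.10.4 does not say where they count.

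**7. Why by-visit QTcF tables do not give an any-time rate.** One patient can appear at several visits, and different patients can appear at different visits, so visit counts cannot be added. Protocol 5.2 reports about 20% of earlier patients with QTc prolongation at some time during treatment. Assume, for illustration only, that this rate applies, with one episode per patient and all 40 still on study: 8/40 = 20%. Even if every episode fell at a scheduled visit, the highest single-visit figure could lie anywhere from 1/40 = 2.5% (one at each of the eight visits from Cycle 1 Day 1 to Cycle 7 Day 1) to 20% (all at one visit).

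**The case against.** The strongest reply is that SAP 3.10 speaks of visits and most naturally governs rows in by-visit displays. The displays in 3.10.2, 3.10.3 and 3.10.4 are largely organised by visit. The literal result for adverse events is implausible, which favours the by-visit reading for laboratory data as well. The worst-grade wording in 3.10.2 is the more specific rule. The SAP introduction follows protocol Amendment 4, and SAP 3.1.2 declares changes only for the primary and secondary analyses, so protocol 13.4.6.5 should still hold for safety.

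Much of this stands as evidence of intent. It does not remove the problem: the by-visit limit is not stated anywhere in SAP 3.10, and general references to the protocol do not override an express sentence.

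The reply is stronger on QTcF. By-visit categories contradict nothing in the SAP, the protocol already commits to a separate QTc summary, and its form may be in the table list, which is not available. The adverse event route, including the signs-and-symptoms limb, covers many off-schedule ECGs. The weekly ECGs after restart are required by the protocol and are not clearly unscheduled. A reader might infer that off-schedule QTc prolongation would go unreported, or that no any-time summary is planned. The documents support neither. They show only that the SAP text does not specify one.

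**Conclusion.** The point holds and is minor. Read literally, SAP 3.10 conflicts with the SAP's worst-grade shift tables and with the protocol's worst on-study grade and Grade 3 or higher laboratory incidence. Any error is downward or nil, at 2.5 percentage points per affected patient on the assumption that all 40 planned patients are in the denominator. The number affected cannot be estimated, so a reader should not infer any particular total understatement.

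A reader might also infer that the SAP intends to drop adverse events found at unscheduled visits. That follows only from the literal wording. It sits badly with the recording requirement in protocol 11.2 and is better taken as a sign that the sentence is too broad.

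The QTcF issue is a separate gap: the SAP text specifies no any-time incidence by its own categories and does not place the weekly post-restart ECGs. All values remain in listings, and efficacy is not affected.

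**What to change.** - In SAP 3.10, limit the exclusion of unscheduled visits to by-visit descriptive summaries.
- State that adverse event tables, worst-grade shift tables and Grade 3 or higher laboratory incidence use all post-baseline on-treatment data, scheduled or unscheduled.
- In SAP 3.10.4, specify the protocol's separate QTc summary as one per-patient table of maximum post-baseline QTcF and maximum change from baseline. Use all ECGs, including symptom-triggered and weekly post-restart recordings, with the existing categories.

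The cost is SAP wording, one added table and a little programming. The data are already collected and listed, and no clinical rule changes.
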